## 8.3. Analysis Conventions

#### 8.3.1. Analysis Sets

#### 8.3.1.1. Efficacy

The primary analysis set for efficacy analysis is the Full Analysis Set (FAS), defined as all participants who are enrolled and have received at least 1 dose of study drug. Participants will be analyzed according to the treatment(s) to which they were assigned.

#### 8.3.1.2. Safety

The primary analysis set for safety analyses is the Safety Analysis Set, defined as all participants who have received at least 1 dose of study drug. Participants will be analyzed according to the treatment(s) they actually received.

#### 8.3.1.3. Pharmacokinetics

The PK Analysis Set will include all enrolled participants who took at least 1 dose of study drug and have at least 1 nonmissing concentration value reported by the PK laboratory.

#### 8.3.1.4. Biomarkers

The Biomarker Analysis Set will include all enrolled participants who took at least 1 dose of the study drug and have at least 1 nonmissing biomarker value for each respective biomarker.

#### 8.3.1.5. Data Handling Conventions

For the primary efficacy endpoint and the categorical secondary efficacy endpoints, missing data will be handled using a missing = failure approach. For continuous secondary endpoints, a missing = excluded approach will be employed.

For selected analyses, HBsAg and HBV DNA data (IU/mL) will be transformed to the logarithmic (base 10) scale (log10 IU/mL).

For summary statistics, PK concentration values below the limit of quantitation will be treated as zero at predose and one-half of the LLOQ for postdose time points.

#### 8.4. Demographic and Baseline Characteristics Analysis

Demographic and baseline measurements will be summarized by cohort using standard descriptive methods.

Demographic summaries will include sex, race/ethnicity, randomization stratification group (if applicable), and age.

Baseline data will include a summary of body weight, height, body mass index, HBsAg ( $log_{10}$  IU/mL), HBv DNA ( $log_{10}$  IU/mL), HBeAg/HBeAb status, HBV genotype, ALT, and additional endpoints as necessary.

#### 8.5. Efficacy Analysis

## 8.5.1. Primary Analysis

The primary analysis will be performed separately for each cohort when the last participant in each cohort reaches FU Week 24.

The proportion of participants who achieve functional cure at FU Week 24 will be analyzed for each treatment cohort. A point estimate with a 2-sided 95% exact CI will be constructed for the proportion using the binomial distribution (Clopper-Pearson method).

## 8.5.2. Secondary Analyses

The secondary efficacy endpoints will be summarized by treatment cohort.

Continuous secondary endpoints will be summarized using conventional descriptive statistics (n, mean, SD, median, first quartile [Q1], third quartile [Q3], minimum, and maximum) by treatment cohort.

Categorical secondary endpoints will be summarized by number and percentage of participants who meet the endpoint by treatment cohort.

## 8.5.3. Analysis of Other Endpoints of Interest

Continuous endpoints will be summarized using conventional descriptive statistics (n, mean, SD, median, Q1, Q3, minimum, and maximum) by treatment cohort.

Categorical endpoints will be summarized by number and percentage of participants who meet the endpoint by treatment cohort.

## 8.6. Safety Analysis

Safety will be evaluated by assessment of clinical laboratory tests and AEs. The primary safety analysis will be evaluated through 30 days posttreatment.

Posttreatment is defined as the following:

- For VIR-2218 and nivolumab, posttreatment will start 4 weeks after last dose.
- For SLGN, posttreatment will start 1 week after last dose.

Posttreatment for each cohort will be based on the last study drug(s) end of the treatment window duration that is the longest.

The safety analysis will also be conducted through FU Week 24 as a secondary safety analysis.

All safety data collected during the study will be included in data listings.

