# **Treatment assessments include:**

- Vital signs
- Weight
- Review AEs
- Review concomitant medications
- Complete Physical Examination
- Symptom-directed physical examination
- 12-Lead ECG (Participants must rest quietly in the supine position for a minimum of 5 minutes prior to the recording)
- Symptoms-directed ophthalmologic examination
- Sample collection for:
  - Safety laboratory tests (hematology and chemistry; coagulation)
  - APRI and FibroTest
  - Quantitative plasma HBV DNA
  - Quantitative serum HBsAg, HBcrAg, HBeAg, and HBV RNA
  - Qualitative HBV serology HBeAg, HBeAb, and HBsAg, HBsAb
  - Collection of PBMC, whole blood, serum, and plasma samples for biomarker analysis
  - Sparse PK samples
  - Urine pregnancy test (females of childbearing potential only)
  - Urinalysis
  - Estimated CLcr (using Cockcroft-Gault method)

Test Product, Dose, and Mode of Administration:	Selgantolimod will be supplied as tablets in strengths of 1.5 mg. SLGN 3 mg (2 × 1.5-mg tablets) will be administered while fasting, once a week, on the same day. Participants must be fasting for at least 8 hours overnight (no food or drinks, except water) and continue through the morning, with no food or drinks, including water, 1 hour before to 2 hours after dosing. After 2 hours postdose, water is allowed and after 4 hours postdose, participants are allowed food and drinks. Participants should take their other prescribed medications, including NUC treatment, no earlier than 2 hours after SLGN dosing or, if medications require dosing with food, no earlier than 4 hours after SLGN dosing.  VIR-2218, 200 mg/mL, solution for injection will be supplied as 0.5 mL single dose vials. VIR-2218 200 mg (2 × 0.5 mL solution) will be administered SC.  Nivolumab (Opdivo®) 40 mg/4 mL solution for injection was supplied as single dose vials. Nivolumab 0.3 mg/kg was administered as IV infusion over 45-60 minutes.  TAF 25-mg tablet orally once daily with food.
Reference Therapy, Dose, and Mode of Administration:	None

Criteria for Evaluation:			
Safety:	Safety will be evaluated by assessment of clinical laboratory tests and AEs collected through FU Week 48. The primary safety analysis will be evaluated through 30 days posttreatment of SLGN ± nivolumab ± VIR-2218.		
	Posttreatment is defined as the following:		
	• For VIR-2218 and nivolumab, posttreatment will start 4 weeks after last dose.		
	• For SLGN, posttreatment will start 1 week after last dose.		

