Despite rapid elimination of VIR-2218 from plasma, prolonged presence is anticipated in the liver, based on tissue PK of VIR-2218 in nonclinical species and data from other GalNAc-conjugated siRNA molecules {Janas 2018}. Since no direct measurement of liver PK was available from human participants in the study, liver PK data from nonclinical studies were initially used to predict human liver PK based on allometric scaling. Using a model describing the onset, peak, and durability of PD response for a chemically similar ESC-GalNAc-siRNA {Attarwala 2017} and available rat tissue PK data for VIR-2218, the human liver half-life of VIR-2218 was previously estimated to be approximately 40 days. An updated analysis was conducted using measured HBsAg following VIR-2218 treatment in participants with chronic HBV infection (from Study VIR-2218-1001 Parts B and C). A sequential PK-PD modeling approach was applied to estimate PK parameters of VIR-2218 in plasma, then an effect compartment representing the site of drug action in liver was used to link the plasma PK and HBsAg reduction observed over time in an indirect response PK-PD model. The PK-PD model described the observed VIR-2218 plasma PK and HBsAg data well and predicted a half-life of approximately 80 days in the liver.

The liver half-life of VIR-2218 of 80 days was used to estimate VIR-2218 liver tissue exposure in humans (Table 3). The median liver exposures for the proposed VIR-2218 doses (6 doses of 200 mg given every 4 weeks) are estimated to not exceed the projected liver exposure of the highest dose at which the safety and tolerability of VIR-2218 has been demonstrated (ie, 900 mg single dose).

Table 3. Estimated Median VIR-2218 Liver Tissue Exposure in Humans Based on PK-PD Model

Simulated Dosing Regimen	C max (µg/g)	AUC (h*μg/g)
900 mg single dose	61.1	34,300 (135,000) a
200 mg Q4W × 6	52.9	34,100 b

PD = pharmacodynamics; PK = pharmacokinetics; Q4W = once every 4 weeks

- a For single dose regimens, partial AUClast up to Day 29 is presented; AUCinf is also presented in parenthesis.
- b For multiple dose regimens, AUC refers to AUClast during the 28-day dosing interval following 2 or 6 doses of VIR-2218.

Taken together, the observed safety and tolerability of VIR-2218, in conjunction with estimations of VIR-2218 liver exposure, support the VIR-2218 regimen selected for this study

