### 3.4. Duration of Treatment.

The duration of study treatment are as follows:

- TAF 25-mg tablet will be administered orally once daily up to 84 weeks (inclusive of 48 Week FU), as applicable, in Cohort 1.
- VIR-2218 200 mg SC will be administered once every 4 weeks for 24 weeks (6 doses).
- Nivolumab 0.3 mg/kg IV will be administered once every 4 weeks for up to 24 weeks (up to 6 doses).
- SLGN 3 mg ( $2 \times 1.5$ -mg tablets) will be administered orally while fasting once a week on the same day for up to 24 weeks (up to 24 doses).

After completing study treatments all participants will undergo 48 weeks of FU.

NOTE: Nivolumab dosing was stopped in this study and all treatments in Cohort 2 Group B were discontinued. Rationale is provided in Section 1.3.1.

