#### **8.6.2.** Adverse Events

Clinical and laboratory AEs will be coded using the MedDRA. System organ class, high-level group term (HLGT), high-level term (HLT), preferred term (PT), and lower-level term (LLT) will be attached to the clinical database.

Events will be summarized on the basis of the date of onset for the event. A treatment-emergent AE (TEAE) will be defined as:

- Any AE that begins on or after the date of first dose of any study drug and no later than 30 days posttreatment of SLGN + nivolumab ± VIR-2218
- Any AE leading to premature discontinuation of any study drug

Summaries (number and percentage of participants) of TEAEs (by SOC and PT) will be provided by treatment group:

- All TEAEs
- TEAEs of Grade 3 or higher
- All TE treatment-related AEs
- TE treatment-related AEs of Grade 3 or higher
- All TE SAEs
- All TE treatment-related SAEs
- All TEAEs leading to premature discontinuation of any study drug
- All TEAEs leading to temporary interruption of any study drug
- AEs of special interest (eg, uveitis)

Summaries (number and percentage of participants) of all on-treatment and posttreatment potential irAEs (by SOC and PT), as defined by relevant MedDRA Standardised MedDRA Queries (SMQs), will be provided by treatment group.

All AEs collected during the study will be presented in the data listings.

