## 8.6.3. Laboratory Evaluations

Selected laboratory data (using units) will be summarized using only observed data. Data and change from baseline at all scheduled time points will be summarized.

Graded laboratory abnormalities will be defined using the grading scheme in Appendix 11.5.

Incidence of TE laboratory abnormalities, defined as values that increase at least one toxicity grade from baseline at any time postbaseline up to 30 days posttreatment of  $SLGN + nivolumab \pm VIR-2218$ , will be summarized by treatment group. If baseline data are missing, then any graded abnormality (ie, at least a Grade 1) will be considered TE.

This analysis will also be provided through FU Week 24.

All laboratory abnormalities will be included in the listings of laboratory data.

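### The protocol specifies no general AE, SAE, Grade 3+ or graded-laboratory incidence summary for FU Weeks 24 to 48, although safety data are collected to FU Week 48

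*Supplement*

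**What the plan says.** The synopsis (Criteria for Evaluation, Safety) gives the data horizon: "Safety will be evaluated by assessment of clinical laboratory tests and AEs collected through FU Week 48". Section 3.4 confirms it: "After completing study treatments all participants will undergo 48 weeks of FU". Section 6.7 schedules safety laboratories up to that visit.

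The analysis windows are shorter.

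- Section 8.6, primary: "The primary safety analysis will be evaluated through 30 days posttreatment".
- Section 8.6, secondary: "The safety analysis will also be conducted through FU Week 24 as a secondary safety analysis".
- Section 8.6.2 defines a TEAE as an AE starting on or after first dose and "no later than 30 days posttreatment of SLGN + nivolumab ± VIR-2218". A second limb, with no time limit, adds any AE that ends a study drug early. The tables of all AEs, Grade 3+ AEs and SAEs rest on this definition.
- Section 8.6.3 defines treatment-emergent graded abnormalities up to the same 30-day point, then adds: "This analysis will also be provided through FU Week 24".

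For data outside these windows the stated destination is the listings. For AEs, section 8.6.2 says: "All AEs collected during the study will be presented in the data listings". Section 8.2.2 plans a final analysis at the end of the study but names no safety tables or windows for it.

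**The concern.** The part of follow-up without a general incidence table is one in which the protocol itself foresees liver events. Section 3.5 puts everyone not on TAF at end of treatment into treatment-free follow-up, and lets participants who had already stopped NUC stay off it. Table 7 in section 7.7.5 exists because HBV DNA and ALT may rebound there. It carries no Week 24 limit, and one of its criteria needs more than 8 weeks of raised ALT before it is met. Section 7.7.4 warns that immune-related events can arise many months after the last nivolumab dose. After stopping nivolumab, the sponsor kept all participants in follow-up to Week 48 (section 1.5).

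If the final report follows section 8.6 as written, a first Grade 4 ALT rise or an SAE at FU Week 36 would not enter the general incidence percentages. A reader of those tables would see off-treatment safety for only half of the period in which it was observed.

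**Working it through.** There is no sample-size or power figure to reproduce here. The check is calendar arithmetic plus a comparison of the planned outputs.

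**1. Timeline.** Treatment of 36 weeks (Cohort 1 and Group A) plus 48 weeks of follow-up gives 36 + 48 = 84 weeks. This matches the maximum TAF duration in section 3.4.

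**2. End of the primary window.** Under section 8.6, posttreatment starts at the latest of last VIR-2218 or nivolumab dose + 4 weeks and last SLGN dose + 1 week. Dose weeks come from section 6.5, for a participant who completes the schedule.

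- Cohort 1 and Group A: VIR-2218 20 + 4 = 24; SLGN 35 + 1 = 36. Posttreatment starts at Week 36. The original nivolumab schedule, 32 + 4 = 36, gives the same week.
- Group B, original schedule: nivolumab 20 + 4 = 24; SLGN 23 + 1 = 24. Posttreatment starts at Week 24.
- Adding 30/7 = 4.3 weeks, the window closes at about FU Week 4.3 in each case.

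**3. What the secondary window leaves out.** 48 − 24 = 24 weeks, or 50% of follow-up. Safety laboratories fall at FU Weeks 4, 12, 24, 36 and 48, so 2 of 5 visits (40%) lie beyond it.

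**4. VIR-2218 persistence (Cohort 1 and Group A only; Group B received none).** The last dose is at Week 20. Section 1.4.4 reports a model that "predicted a half-life of approximately 80 days in the liver", after a previous estimate of about 40 days. The fraction remaining is 0.5^(days since last dose / half-life).

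| Time point | Days | 80-day half-life | 40-day half-life |
|---|---|---|---|
| End of primary window | 142 | 29% | 8.5% |
| FU Week 24 | 280 | 8.8% | 0.8% |
| FU Week 48 | 448 | 2.1% | 0.04% |

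Most of the modelled washout is over by FU Week 24. Drug persistence is therefore a minor argument for the later window; time off NUC is the main one.

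**5. Would there be anything to count?** The documents give no late-flare rate, so these rates are assumptions. The chance of at least one such event is 1 − (1 − p)^n.

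| Assumed rate in FU Weeks 24-48 | n = 40 (Group A) | n = 60 (Cohort 2) |
|---|---|---|
| 1% | 33% | 45% |
| 2% | 55% | 70% |
| 5% | 87% | 95% |
| 10% | 98.5% | 99.8% |

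The planned group sizes are upper limits for the number still off NUC and under observation.

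**6. Outputs that reach past FU Week 24, and what each leaves uncounted.**

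- Potential-irAE table (8.6.2): covers posttreatment events with no stated cut-off, but only those matching the chosen SMQs.
- By-visit laboratory summaries (8.6.3): selected tests at scheduled time points. A maximum shows one extreme value, not how many participants had one, and results from unscheduled flare visits fall outside.
- Discontinuation limb of the TEAE definition (8.6.2): late in follow-up this can apply to Cohort 1 participants taking TAF. An AE that stops TAF at FU Week 40 is a TEAE; a Grade 4 ALT rise at the same week in an off-NUC Cohort 2 participant is not.
- Off-NUC endpoint (8.1.3): records NUC starts, not the grade or seriousness of the event behind them.

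None yields the number of participants with a first Grade 3-4 ALT or bilirubin abnormality, an SAE or a Grade 3+ AE in FU Weeks 24-48.

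**The case against.** The strongest objection is that only the protocol is shown. Appendix 11.2 refers to a statistical analysis plan, and the tables for a planned final analysis are commonly set there. The synopsis also says, without a week limit, that AEs and laboratory abnormalities will be summarized by counts and percentages. This stands as a limit: FU Week 48 tables may exist in the SAP. It does not remove the point, because the protocol does not leave the windows open. It names two and stops at FU Week 24.

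A reader might infer that late liver events would appear only in listings, or be missing from every percentage. The documents do not support that, given the four outputs in step 6 of the working. Nor does saying that all data are listed mean that they are only listed.

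A reader might also extend the flare concern to all of about 100 participants. That is too wide. Cohort 1 participants on TAF stay on it through follow-up.

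Finally, a secondary window that matches the FU Week 24 efficacy endpoint is coherent in a descriptive Phase 2a study, and listings of this size can be read. That supports keeping the FU Week 24 tables, but gives no reason to omit the later ones.

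**Conclusion.** The point holds in limited form. As written, sections 8.6, 8.6.2 and 8.6.3 specify no general incidence summary of AEs, Grade 3+ AEs, SAEs or treatment-emergent graded laboratory abnormalities beyond FU Week 24. The gap is 24 of 48 follow-up weeks and 2 of 5 safety-laboratory visits. It matters mainly for Cohort 2 and for Cohort 1 participants who had already stopped NUC.

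It would be tempting to say that off-treatment risk will be understated by half. That would require flares to be spread evenly over follow-up, and the documents give neither a rate nor a time pattern. What can be said is that any first Grade 3-4 ALT or bilirubin abnormality, SAE or Grade 3+ AE in that period has no planned general count, apart from AEs captured by the discontinuation limb. This rests on the protocol text alone and would fall away if the SAP already specifies the tables.

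**What to change.** In sections 8.2.2, 8.6 and 8.6.3, state that at the final analysis the existing tables of all AEs, Grade 3+ AEs, SAEs, AEs of special interest and graded laboratory abnormalities are repeated through FU Week 48, by cohort and, within Cohort 2, by group. Section 8.6.2 should say that these repeats are not bound by the 30-day TEAE limit. Keep the 30-day and FU Week 24 tables unchanged. If the SAP already contains the tables, a cross-reference is enough.

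Any display by NUC status should be descriptive only and use status at event onset. NUC status is a post-baseline variable that a flare can itself change through Table 7, and the cells will be small.

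The cost is one more run of existing tables at an analysis already planned, with no new data, visits or change to clinical management. The small downside is that some unrelated late AEs enter the FU Week 48 tables.

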## 8.6.1. Extent of Exposure

A participant's extent of exposure to study drug data will be generated from the study drug administration data. Exposure data will be summarized by treatment cohort.

#### **8.6.2.** Adverse Events

Clinical and laboratory AEs will be coded using the MedDRA. System organ class, high-level group term (HLGT), high-level term (HLT), preferred term (PT), and lower-level term (LLT) will be attached to the clinical database.

Events will be summarized on the basis of the date of onset for the event. A treatment-emergent AE (TEAE) will be defined as:

- Any AE that begins on or after the date of first dose of any study drug and no later than 30 days posttreatment of SLGN + nivolumab ± VIR-2218
- Any AE leading to premature discontinuation of any study drug

Summaries (number and percentage of participants) of TEAEs (by SOC and PT) will be provided by treatment group:

- All TEAEs
- TEAEs of Grade 3 or higher
- All TE treatment-related AEs
- TE treatment-related AEs of Grade 3 or higher
- All TE SAEs
- All TE treatment-related SAEs
- All TEAEs leading to premature discontinuation of any study drug
- All TEAEs leading to temporary interruption of any study drug
- AEs of special interest (eg, uveitis)

Summaries (number and percentage of participants) of all on-treatment and posttreatment potential irAEs (by SOC and PT), as defined by relevant MedDRA Standardised MedDRA Queries (SMQs), will be provided by treatment group.

All AEs collected during the study will be presented in the data listings.

## 8.6.3. Laboratory Evaluations

Selected laboratory data (using units) will be summarized using only observed data. Data and change from baseline at all scheduled time points will be summarized.

Graded laboratory abnormalities will be defined using the grading scheme in Appendix 11.5.

Incidence of TE laboratory abnormalities, defined as values that increase at least one toxicity grade from baseline at any time postbaseline up to 30 days posttreatment of  $SLGN + nivolumab \pm VIR-2218$ , will be summarized by treatment group. If baseline data are missing, then any graded abnormality (ie, at least a Grade 1) will be considered TE.

This analysis will also be provided through FU Week 24.

All laboratory abnormalities will be included in the listings of laboratory data.

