### 6.5. Treatment Schedule

### **Cohort 1:**

- Baseline/Day 1, Week 4, and Week 8 SC VIR-2218
- Week 12, 16, and 20 SC VIR-2218; add-on IV nivolumab
- Week 24, 28, and 32 IV nivolumab
- Oral TAF dose daily for 36 weeks
- Oral SLGN dose weekly for 24 weeks, starting Week 12 through Week 35

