### 6.7. Follow-up Assessments

The FU assessments have the following visit windows: Cohort 1: Week 1 ( $\pm$  3 days), Weeks 4 to 16 ( $\pm$  5 days), and Weeks 24 to 48 ( $\pm$  14 days); Cohort 2: Weeks 1 ( $\pm$  2 days), and Weeks 4 to 16 ( $\pm$  5 days), and Weeks 24 to 48 ( $\pm$  14 days). FU assessments include the following:

- All participants will complete following FU visits: Weeks 1\*, 4, 8\*, 12, 16\* (for women of childbearing potential), 24 (Primary), 36, and 48
- Vital signs (at Weeks 4 to 48)
- Symptom-directed physical examination (at Weeks 4 to 48)
- Symptom-directed ophthalmologic examination (at Weeks 4 to 48)

\* Treatment Assessments on Week 1 and Week 13 (Phone Call/Virtual Visit)

- Weight (At Week 48 only)
- 12-lead ECG (At Week 48 only)
- Review AEs and concomitant medications (At Week 1\*, 8\*, 16\*, at Weeks 4 to 48)
- Sample collection for:
  - Safety laboratory tests (hematology and chemistry; coagulation) (at Weeks 4 to 48)
  - APRI and FibroTest (at Weeks 12 and 48)
  - Quantitative plasma HBV DNA (at Weeks 4 to 48)
  - Quantitative HBV serum HBsAg, HBcrAg, HBeAg, and HBV RNA (at Weeks 4 to 48)
  - Qualitative HBV serology HBeAg, HBeAb, HBsAg, and HBsAb (at Weeks 4 to 48)
- Urine pregnancy test (females of childbearing potential only, every 4 weeks through Week 48; Week 8 and Week 16 collection will be a virtual/telephonic visit)
- Serum sample for HBV viral sequencing and genotyping sample (baseline) (at Weeks 4 to 48)
- Estimated CLcr (using Cockcroft-Gault method) (at Week 48 only)

\*FU Visit Week 1, Week 8, and Week 16 (Phone Call/Virtual Visit)

The following evaluations are to be completed at the FU Week 1 phone call or virtual visit:

- Review of AEs and concomitant medications
- Review of laboratory results from EOT visit to determine entry into TFFU

Participants who discontinue the study treatment(s) prematurely will be followed for the reminder of the study according to the defined study visits and procedures.

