Biomarker Samples: Collection of PBMC, whole blood, serum, and plasma samples for biomarker analysis l, m		X			X 		X					X m								X		
Sparse PK for VIR-2218 n		X			X				X													
Sparse PK for SLGN n					X				X			Х										
Estimated creatinine clearance (using the Cockcroft-Gault method)	X	X			X								X	Х								X
Urinalysis	X	X	X	X	X			X	X	X	X	X	X	X								
Urine Drug and Alcohol Screen	X																					
Autoantibodies	X																					
TSH	X									X			X	Х								
FSH°	X																					
Serum Pregnancy Test p	X													X								
Urine Pregnancy Test p		X	X	X	X			X	X	X	X	X	X			X	Xp	X	Xp	X	X	X
Enrollment		X																				
Dispense and Administer TAF as appropriate							Ten	ofovir	alafen	amide	(TAF	) 25-m	g tablet admi	nistered	orally d	aily for u	up to 84	weeks				
Dispense & Administer VIR-2218 SC as appropriate		X	X	X	X			X	X													
Dispense & Administer SLGN q as appropriate					X	X	X	X	X	X	X	X										

	Screening	Baseline				Tı W	reatm Veek (	ent Cy ± 2 da	vcles ys) a				EOT (-5 days)				]	Follow-u	p Week	S b		
	(45 days)		4	8	12	13 c	14	16	20	24	28	32	36/EOT	EDd	1°	4	8°	12	16 c	24	36	48
Study Drug Accountability			X	X	X		X	X	X	X	X	X	X									
CCI																						
CCI																						
CCI																						

AE = adverse event; APRI = AST to Platelet Ratio Index; CT = computed tomography; ddPCR = digital droplet polymerase chain reaction; ECG = electrocardiogram; ED = early discontinuation; EOT = end of treatment; FSH = follicle-stimulating hormone; FU = follow-up; HBcrAg = hepatitis B core-related antigen; HBeAb = hepatitis B e antibody; HBeAg = hepatitis B e antigen; HBsAb = hepatitis B surface antibody; HBsAg = hepatitis B surface antigen; HBV = hepatitis B virus; HCC = hepatocellular carcinoma; HCV = hepatitis C virus; HDV = hepatitis D virus; IV = intravenous; PBMC = peripheral blood mononuclear cells; PK = pharmacokinetic; SAE = serious adverse event; SC = subcutaneous; SLGN = selgantolimod; TAF = tenofovir alafenamide; TSH = thyroid-stimulating hormone

- a All study visits except for Weeks 13 and 14.
- b FU Week 1 will have a visit window of + 3 days, FU Weeks 4 through FU Week 16 will have a visit window of ± 5 days, and FU Weeks 24 through FU Week 48 will have a visit window of ± 14 days.

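### The 30-day cut-off for treatment-emergent laboratory abnormalities falls inside the FU Week 4 visit window, so some compliant but late samples miss the primary table

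*Supplement*

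**What the plan says.** Section 8.6 fixes the period: "The primary safety analysis will be evaluated through 30 days posttreatment". It then says when posttreatment begins for each drug: "For SLGN, posttreatment will start 1 week after last dose", and "For VIR-2218 and nivolumab, posttreatment will start 4 weeks after last dose". Where a cohort receives several drugs, the latest of these dates governs: "Posttreatment for each cohort will be based on the last study drug(s) end of the treatment window duration that is the longest".

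Section 8.6.3 applies the 30-day limit to laboratory data and counts "values that increase at least one toxicity grade from baseline at any time postbaseline up to 30 days posttreatment". It also repeats the incidence analysis through FU Week 24, summarizes laboratory data at every scheduled time point, and lists all abnormalities.

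The visit calendar is set in Sections 6.5 to 6.7 and Appendix 11.3. For Cohort 1, Section 6.5 gives "Oral SLGN dose weekly for 24 weeks, starting Week 12 through Week 35". Cohort 2 Group A has the same SLGN schedule, and Group B was planned to end SLGN at Week 23. Appendix 11.3 says that "FU Weeks 4 through FU Week 16 will have a visit window of ± 5 days". Section 6.7 lists the remote contacts: "FU Visit Week 1, Week 8, and Week 16 (Phone Call/Virtual Visit". Neither procedures table marks safety laboratory tests at FU Week 8.

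**The concern.** Safety and tolerability is the first-listed primary objective, and the 30-day period is the primary safety analysis. FU Week 4 is the only scheduled blood draw after the EOT visit that can enter that period. The laboratory limit is set by day and the sample is scheduled by visit, with a tolerance that extends past the limit. Two participants who both comply, one sampled on day 30 and one on day 31, are therefore treated differently in the primary laboratory table.

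The table shows the second participant as having no late abnormality, when that participant simply had no draw between EOT and the limit. This matters most for rebound after treatment stops, which the protocol monitors closely (Section 7.7.5).

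**Working it through.** **Inputs**

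- Last SLGN dose: Week 35 (Cohort 1, Group A) or Week 23 (Group B as planned), Section 6.5.
- Last VIR-2218 dose: Week 20 (Cohort 1, Group A), Section 6.5.
- Last nivolumab dose as planned: Week 32 (Cohort 1, Group A) or Week 20 (Group B), Section 6.5.
- Posttreatment start: 1 week after SLGN, 4 weeks after VIR-2218 or nivolumab, whichever is latest, Section 8.6.
- FU Week 4 and FU Week 12 tolerance: ± 5 days, Section 6.7 and Appendix 11.3.
- EOT tolerance: ± 5 days in Section 6.6, −5 days in the tables of Appendix 11.3.

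**Step 1: check the anchor.** Section 3.4 gives TAF for up to 84 weeks including the 48-week FU. 36 + 48 = 84, so FU weeks count from EOT at Week 36. Weekly SLGN from Week 12 through Week 35 is 24 doses, as stated.

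**Step 2: posttreatment day 0.**

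- Cohort 1 and Group A: max(20 + 4, 32 + 4, 35 + 1) = Week 36. With nivolumab stopped, max(20 + 4, 35 + 1) = Week 36 still.
- Group B as planned: max(20 + 4, 23 + 1) = Week 24.

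Both are the nominal EOT.

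**Step 3: place the samples.** FU Week 4 is day 28 ± 5, so days 23 to 33. The limit is day 30. Days 23 to 30 are counted (8 of 11 allowed days, including target day 28), and days 31 to 33 are not (3 of 11). FU Week 12 is day 84 ± 5, so days 79 to 89.

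**Step 4: share affected.** Let EOT fall *a* days from nominal and FU Week 4 fall *b* days from its target, with *b* from −5 to +5. The sample is on day 28 + *a* + *b* and is excluded when *a* + *b* ≥ 3. The documents give no distribution of visit dates, so I assume that all allowed combinations are equally likely.

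| EOT model | FU Week 4 range | Sample excluded | No draw after day 0 and by day 30 |
|---|---|---|---|
| On time (*a* = 0) | days 23–33 | 3/11 = 27.3% | 3/11 = 27.3% |
| *a* from −5 to 0 (Appendix 11.3) | days 18–33 | 6/66 = 9.1% | 6/66 = 9.1%, about 4 of 40 |
| *a* from −5 to +5 (Section 6.6) | days 18–38 | 36/121 = 29.8% | 6/121 = 5.0%, about 2 of 40 |

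In the last row, 30 of the 36 excluded combinations have *a* > 0 (4 + 5 + 6 + 7 + 8 for *a* = 1 to 5). In those, the EOT blood is drawn on posttreatment days 1 to 5 and enters the primary period. The 6 that remain are 3 with *a* = 0, 2 with *a* = −1 and 1 with *a* = −2. If a draw on day 0 counts as posttreatment, the last column falls to 0, to 3/66 (4.5%, about 2 of 40) and to 3/121 (2.5%, about 1 of 40).

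**Step 5: sensitivity to the anchor.** If FU weeks counted from the last SLGN dose, FU Week 4 would be days 16 to 26 and the problem would not arise.

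**Step 6: Group B participants stopped early.** Section 3.2.1 makes their next visit the EOT. Assume an EOT visit 4 weeks after the last SLGN dose. If nivolumab was last given a cycle before that SLGN dose, posttreatment starts 7 days after the SLGN dose and FU Week 4 is day 28 + 28 − 7 = 49 ± 5, days 44 to 54. If both drugs were last given on the same day, posttreatment starts at 28 days and FU Week 4 is back at days 23 to 33. The actual timing is not in the document.

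**The case against.** The strongest reply is that nothing goes unreported. The same incidence is produced through FU Week 24, a longer period that contains the first. FU Week 4 also appears in the by-visit summaries whatever its day, and every abnormality is listed. Section 7.7.5 provides for unscheduled draws in ALT monitoring, which may fall between FU Weeks 4 and 12. The study is open-label and its safety summaries are descriptive. A day-32 value lies outside a 30-day period by definition. Visit windows are commonly left to the SAP, and only the protocol was available here.

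Most of this stands, and it makes the point minor. It does not remove it. The protocol itself states a cut-off that cuts through its own visit window. The FU Week 24 analysis answers a question about a much longer period and does not replace a near-treatment incidence. Unscheduled draws are not systematic.

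A reader might infer more than the documents support:

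- **That on-schedule FU Week 4 samples are dropped in general.** With EOT on time, a sample on target day 28 is kept. Only the last three allowed days are lost.
- **That every participant with an excluded sample has no posttreatment laboratory value.** The shares of 9% to 30% correspond to about 4 to 12 excluded samples per 40. Under the Section 6.6 window most of those participants have a late EOT draw that is itself posttreatment.
- **That safety data are lost.** The values remain in three other outputs.

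**Conclusion.** The point holds as a minor one. The day-30 limit in Section 8.6.3 lies inside the allowed FU Week 4 window of days 23 to 33, so some compliant but late samples do not enter the primary 30-day laboratory incidence, and no scheduled draw follows until FU Week 12.

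Under an even spread of visits, the affected share of FU Week 4 samples is 27% with EOT on time, 9% with the Appendix 11.3 EOT window and 30% with the Section 6.6 window. Clustering around the target day would lower all three. Participants with no draw after day 0 inside the period number about 2 to 4 of 40 under the two EOT-window models, or 3 in 11 if every EOT is exactly on time.

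The result rests on FU weeks counting from EOT, which the 84-week total implies but no section states outright, and on completion of the planned dosing schedule. The effect is under-ascertainment in one table.

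**What to change.** In Section 8.6.3, or in the SAP, count laboratory values up to 30 days posttreatment or through the FU Week 4 visit if it is done within its allowed window, whichever is later. Apply the same rule in every cohort. Leave the 30-day limit for adverse events in Section 8.6.2, because those are dated by onset.

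Two clarifications belong with it. State that FU weeks count from EOT. Reconcile the EOT window between Section 6.6 (± 5 days) and Appendix 11.3 (−5 days), since the number of excluded samples depends on it.

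The cost is one sentence and no new data. The laboratory period can run a few days past the adverse-event period and will vary slightly between participants, so an ALT rise on day 32 could be treatment-emergent in the laboratory table without a matching treatment-emergent adverse event. For Group B participants stopped early the extension could be longer (up to day 54 under the assumed timing above), which a footnote to the table should state. The reported incidence may come out slightly higher.
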